9.7.1.8.1 EXTENT OF EXPOSURE

Extent of exposure will be summarized by categories of cumulative weeks as well as by categories of duration of exposure. The number and percentage of subjects for each exposure category will be presented by treatment group. Duration of exposure is the number of days between the date the subject received the first dose of study drug and the date the subject received the last dose of study drug and will be summarized using descriptive statistics for continuous variable by treatment group. Overall exposure (number of subject-weeks) is

defined as summation over all subjects' exposure durations and will be summarized by treatment group.

9.7.1.8.2 ADVERSE EVENTS

The AE verbatim descriptions (investigator terms from the eCRF) will be classified into standardized medical terminology using the Medical Dictionary for Regulatory Activities (MedDRA). Adverse events will be coded to the MedDRA (Version 19.0 or higher) lower level term (LLT) closest to the verbatim term. The linked MedDRA preferred term (PT) and primary system organ class (SOC) are also captured in the database.

A TEAE is defined as:

- An AE that emerges on or after start of study treatment or within 28 days following the last dose of study drug, having been absent at pretreatment (Baseline) or
- Reemerges on or after start of study treatment, having been present at pretreatment (Baseline) but stopped before treatment, or
- Worsens in severity on or after start of study treatment relative to the pretreatment state, when the AE is continuous.

Only those AEs that are treatment-emergent will be included in summary tables. All AEs, treatment-emergent or otherwise, will be presented in subject data listings.

The TEAEs will be summarized by treatment group on the Safety Analysis Set. The incidence of TEAEs will be reported as the number (percentage) of subjects with TEAEs by SOC and PT. A subject will be counted only once within an SOC and PT, even if the subject experienced more than 1 TEAE within a specific SOC and PT. The number (percentage) of subjects with TEAEs will also be summarized by maximum severity (mild, moderate, or severe). The number (percentage) of subjects with TEAEs will also be summarized by relationship to study drug.

The number (percentage) of subjects with treatment-related TEAEs, treatment-emergent serious adverse events (SAEs) and TEAEs leading to discontinuation from study drug will be also summarized by SOC and PT. Subject data listing for each above type of AEs and AEs leading to death will also be provided.

AEs will be summarized by the following subgroups: region, treatment with AChEIs (no or yes), and treatment with memantine (no or yes). (revised per Amendment 03)

9.7.1.8.3 LABORATORY VALUES

Laboratory results will be summarized using International System of Units, as appropriate.

Laboratory test results will be assigned a low/normal/high (LNH) classification according to whether the value was below (L), within (N), or above (H) the laboratory parameter's reference range. Within-treatment comparisons for each laboratory parameter will be based on 3-by-3 tables (shift tables) that compare the baseline LNH classification to the LNH classification at each postbaseline visit and at the end of treatment. Similar shift tables will also compare the

baseline LNH classification to the LNH classification for the highest and lowest value during the treatment period.

[Appendix 2](#) (Sponsor's Grading for Laboratory Values) presents the criteria that will be used to identify subjects with treatment-emergent markedly abnormal laboratory values (TEMAVs). Except for phosphate, a TEMAV is defined as a postbaseline value with an increase from baseline to a Grade of 2 or higher. For phosphate, a TEMAV was defined as a postbaseline value with an increase from baseline to a Grade of 3 or higher. When displaying the incidence of TEMAVs, each subject may be counted once in the laboratory parameter high and in the laboratory parameter low categories, as applicable

9.7.1.8.4 VITAL SIGNS

Descriptive statistics for vital signs parameters (ie, systolic and diastolic BP, pulse, respiratory rate, temperature, weight), and changes from baseline will be presented by visit and treatment group.

9.7.1.8.5 ELECTROCARDIOGRAMS

Descriptive statistics for ECG parameters and changes from baseline will be presented by visit and treatment group. ECG interpretation (categorized as normal; abnormal, not clinically significant; and abnormal, clinically significant) will be presented by visit and treatment group using frequency count. The number (percentage) of subjects with post-baseline abnormal ECG result in QTcF will be summarized by treatment group.

9.7.1.8.6 OTHER SAFETY ANALYSES

Columbia Suicide Severity Rating Scale (C-SSRS)

The C-SSRS responses will be mapped to C-CASA (Columbia- classification algorithm of suicide assessment). The incidence of suicidal ideation or suicidal behavior will be summarized by treatment group. Continuous variables will be summarized by descriptive statistics; number of subjects, mean, standard deviation, median, minimum, and maximum and categorical variables by number (percentage) of subjects.

UPDRS-III (Unified Parkinson's Disease Rating Scale Part III: Motor Examination)

Changes from baseline in the total score of UPDRS-III will be summarized using descriptive statistics for continuous variable by visit and treatment group.

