7.1.1 Current Therapeutic Options

There are no therapies currently available that alter the underlying neurodegenerative process of LBD. A number of symptomatic therapies can improve patient quality of life, primarily through management of motor symptoms such as bradykinesia, rigidity and gait disturbance. Levodopa remains the most effective medication available for treating the motor features of Parkinson's disease that occur in LBD. Current therapy for cognitive deficits associated with

LBD is largely based on the use of acetylcholinesterase inhibitors (AChEIs), such as rivastigmine and donepezil. Rivastigmine is approved in multiple countries for symptomatic treatment of cognitive deficits in PDD and donepezil is approved in several Asian countries including Japan and the Philippines for symptomatic treatment of DLB. Memantine is also used in the treatment of DLB but its efficacy is small (Aarsland, et al., 2009). (revised per Amendment 03) With regard to neuropsychiatric symptoms, pimavanserin is approved for these symptoms in Parkinson's disease. AChEIs and antipsychotics such as risperidone, quetiapine, and olanzapine are also commonly used in clinical neurology practice for this purpose. However, the efficacy of AChEI and antipsychotic drugs on cognitive symptoms and neuropsychiatric symptoms is modest. In addition, there are concerns about worsening of parkinsonism by both AChEI and antipsychotics as well as special concerns about hypersensitivity to antipsychotics. Therefore, there is need for further treatment benefit.

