9.7.1.1.2 SECONDARY ENDPOINTS

(Order of secondary endpoints revised per Amendment 05)

- CGIC-DLB at 12 weeks of treatment
- Change from baseline at 12 weeks of treatment in the following endpoints:
 - CFI score
 - MMSE total score
 - NPI total score, subscores and caregiver distress score
- Safety and tolerability of E2027 as measured by (revised per Amendment 02):
 - Incidence of adverse events including severe AEs, serious AEs, AEs resulting in discontinuation (revised per Amendment 02)
 - Incidence of orthostatic hypotension and orthostatic tachycardia (revised per Amendment 02)
 - Incidence of markedly abnormal laboratory values and shifts from baseline of laboratory values (revised per Amendment 02)
 - Incidence of abnormal ECG parameters and abnormal ECG findings (revised per Amendment 02)
 - Incidence of suicidality based on C-SSRS (revised per Amendment 02)
 - Changes from baseline in the total score of UPDRS-III (revised per Amendment 02)

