## **5 STATISTICAL METHODS**

All statistical tests will be 2-sided at the 5% significance level unless otherwise stated. All descriptive statistics for continuous variables will be reported using mean, standard deviation (SD), median, minimum, maximum and number of subjects with non-missing data. Categorical variables will be summarized as number (percentage) of subjects.

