### 5.6.6.2 UPDRS-III

Changes from baseline in the total score and four subscores of UPDRS-III will be summarized using descriptive statistics for continuous variable by visit and treatment group.

This scale evaluates extrapyramidal features in motor function in Parkinson’s disease. It contains 33 items in 18 categories: (1) speech, (2) facial expression, (3) rigidity, (4) finger tapping, (5) hand movements, (6) supinational and pronation movements of hands, (7) toe tapping, (8) leg agility, (9) arising from chair, (10) gait, (11) freezing of gait, (12) postural stability, (13) posture, (14) body bradykinesia, (15) postural tremor of hands, (16) kinetic tremor of hands, (17) rest tremor amplitude and (18) constancy of rest tremor. Each item is scored 0 to 4, giving a total score range 0 to 132. As far as is practical, the motor assessments should be made with the subject in the “on” state at each visit and at the same time relative to the subject’s last dose of Parkinson’s disease medication (such as L-dopa). The four subscores are for tremor, rigidity, bradykinesia and postural instability and gait difficulty (PIGD), as calculated per Section 8.4.

The above summary will be repeated where UPDRS and their subscores will be censored if there are changes in the subjects DLB motor medications, censoring will occur at the date of medication change, no imputations will be made.

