## 5.7 Other Analyses

The following endpoints will be analyzed in the FAS using ANCOVA or GLMM as appropriate, with MI assuming MAR:

Change from baseline in the quality of life endpoints (total score and domain scores of DEMQOL and DEMQOL-Proxy, the EQ-5D and EQ-5D Proxy index scores, and EQ VAS scale) at 12 weeks of treatment

Percent change from baseline in CSF cGMP concentrations after 9 weeks of treatment.

The ANCOVA model will include corresponding baseline as a covariate, with treatment group and randomization stratification variables as factors.

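### UPDRS-III change is a secondary safety endpoint, but no planned output gives an E2027-minus-placebo difference with a confidence interval

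*Protocol*

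**What the plan says.** Protocol 9.7.1.1.2 and SAP 5.1.2 both list "Changes from baseline in the total score of UPDRS-III" as a secondary endpoint, in the safety and tolerability group.

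The planned analysis is descriptive in both documents. Protocol 9.7.1.8.6 states: "Changes from baseline in the total score of UPDRS-III will be summarized using descriptive statistics for continuous variable by visit and treatment group". SAP 5.6.6.2 states: "Changes from baseline in the total score and four subscores of UPDRS-III will be summarized using descriptive statistics". It then adds: "The above summary will be repeated where UPDRS and their subscores will be censored if there are changes in the subjects DLB motor medications". That repeat is made without imputation. SAP section 5 fixes what descriptive means: "All descriptive statistics for continuous variables will be reported using mean, standard deviation", followed by median, minimum, maximum and number of subjects. A between-arm difference and a confidence interval are not on that list.

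Elsewhere in the plan, continuous changes are modelled. CFI, MMSE and NPI have a model-based comparison (SAP 5.4.2). The exploratory quality-of-life scores have one too (SAP 5.7): "The ANCOVA model will include corresponding baseline as a covariate, with treatment group and randomization stratification variables as factors".

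**The concern.** Parkinsonism is one of the core features of the disease (protocol Appendix 1), and the protocol's background section records that with existing symptomatic drugs "there are concerns about worsening of parkinsonism by both AChEI and antipsychotics". The sponsor took motor effects seriously enough to add subscores and a summary censored at motor-drug changes. Yet a single-scale endpoint with a pre-treatment value and a fixed Week 12 visit ends in two columns of raw changes.

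The question for a reader of the safety section is how large a motor worsening the data exclude. A difference with its interval answers that directly, and separate arm means do not. Any interval computed after unblinding would also be open to choices of covariates, analysis set and handling of dropouts that nobody fixed in advance.

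**Working it through.** **The plan's own figure.** Protocol 9.7.2 gives 80 completers per arm and 12% dropout: 80 / (1 − 0.12) = 90.9, so 91 per arm and 182 in total. This reproduces. The documents state no SD, precision, margin or power for UPDRS-III, so the SDs and correlations below are assumptions.

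**Precision available.** The unadjusted 95% half-width for the difference in mean change is t(0.975; 2n − 2) × SD × √(2/n). At n = 80 per arm this is 1.975 × 0.1581 × SD = 0.312 × SD. It is 0.293 × SD at 91 per arm and 0.334 × SD at 70.

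| Assumed SD of change (points) | Half-width at 80 per arm (points) |
|---|---|
| 6 | 1.9 |
| 8 | 2.5 |
| 10 | 3.1 |

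If the observed difference were zero, worsening beyond these values would lie outside the interval. The scale runs from 0 to 132.

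**Gain in standard error from baseline adjustment.** Let s be the common SD at baseline and Week 12, and r their correlation. The variance of raw change is 2s²(1 − r), and the ANCOVA residual variance is s²(1 − r²). The SE ratio is therefore √((1 + r)/2).

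| Assumed r | SE ratio | Reduction |
|---|---|---|
| 0.6 | 0.894 | 11% |
| 0.7 | 0.922 | 8% |
| 0.8 | 0.949 | 5% |
| 0.9 | 0.975 | 3% |

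At SD 8 and r = 0.8 the half-width goes from 2.50 to 2.50 × 0.949 = 2.37 points.

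**Baseline imbalance.** Under the same equal-variance assumption, an arm that starts D points higher is expected to show a raw change lower by (1 − r) × D, with no treatment effect. At SD of change 8 and r = 0.8, s = 8 / √0.4 = 12.6. One standard error of the baseline difference is 12.6 × 0.1581 = 2.0 points, and the resulting bias is 0.2 × 2.0 = 0.4 points. ANCOVA removes this conditional bias.

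**Which pre-treatment value.** Protocol Table 6 schedules UPDRS-III at Screening, Week 12, Follow-Up, Early Discontinuation (ED) and Unscheduled visits. SAP 8.2.1 takes the last non-missing pre-dose value as the safety baseline, so the Screening score serves. MMSE has the same visit pattern and already gets an ANCOVA with baseline and strata.

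**The case against.** The best reply is that the plan is consistent: it models efficacy and describes safety. Laboratory values, vital signs and ECG intervals are also only summarised, UPDRS-III sits with them, and no motor hypothesis or margin is set anywhere. The quality-of-life scores are modelled because their objective is efficacy. The background concern about parkinsonism relates to other drug classes, not to E2027. All of this stands. It makes the gap one of estimation, not a breach of the plan's own logic.

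Three stronger readings are tempting, and the documents do not support them.

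- *The trial will be unable to bound motor worsening.* The planned n, mean and SD by arm yield a crude interval by the formula above.
- *Baseline and strata are ignored.* The outcome is change from baseline. SAP 5.2.4 tabulates baseline UPDRS-III by arm and stratum, so an imbalance would be visible. SAP 5.3.4 provides for safety summaries by stratification factor as appropriate. What is missing is their use in an adjusted comparison.
- *Adjustment matters greatly for precision, and more so under imbalance.* The SE gain is 3% to 11%, and imbalance does not enlarge it. Only a fraction 1 − r of an imbalance reaches the raw comparison.

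A further objection concerns the remedy. The SAP 5.7 ANCOVA cannot be imported unchanged, because it runs in the Full Analysis Set with multiple imputation under MAR. Safety data use the Safety Analysis Set as treated, and the censored UPDRS-III repeat uses no imputation. A Week 12 analysis also misses many early discontinuers, whose ED values are placed by study day in earlier windows (SAP 8.2.2). They may be the subjects who worsened. This also stands, and the remedy has to settle it.

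**Conclusion.** The concern holds as a gap in estimation. A named secondary safety endpoint has no planned between-arm difference or interval, and a crude reconstruction by the reader does not replace a prespecified adjusted estimate. Data already being collected would give an unadjusted half-width of about 0.31 × SD, or 1.9 to 3.1 points for SDs of 6 to 10. Adjustment adds a modest gain in precision and protection against chance imbalance.

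The point sizes rest on assumed SDs and correlations, equal variances at the two visits, and 80 subjects per arm with Week 12 data. The finding that no contrast is planned rests on none of these. The primary results, sample size and success rule are unaffected.

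**What to change.** In protocol 9.7.1.8.6 and SAP 5.6.6.2, keep the descriptive tables and add:

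- An ANCOVA of Week 12 change in UPDRS-III total score in the Safety Analysis Set, with the pre-treatment (Screening) score as covariate and treatment, AChEI use and region as factors.
- The adjusted E2027-minus-placebo difference with a two-sided 95% CI, labelled as estimation, without a significance claim.
- Observed Week 12 data without imputation, in line with the existing UPDRS-III summaries.
- A repeat with the planned censoring at motor-medication changes.
- The ED or end-of-treatment value shown alongside, using the definition in SAP 8.2.2, so that early discontinuers stay in view.

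Protocol 9.1.3 can be read as placing UPDRS-III at Week 6 as well, which Table 6 does not show. The two should be reconciled.

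The cost is a paragraph of SAP text and a few table rows, with no new data. The downside is one or two more safety intervals to interpret, which the estimation-only label addresses.

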9.7.1.9 Other Analyses

The quality of life endpoints (DEMQOL and DEMQOL-Proxy domain scores, and the EQ-5D and EQ-5D Proxy scores) after 12 weeks of treatment and the percentage change from baseline in CSF cGMP concentrations after 9 weeks of treatment will be analysed using ANCOVA or rank-based ANCOVA as appropriate. The ANCOVA model will include baseline as a covariate, with treatment group and randomization stratification variables as factors.

9.7.2 Determination of Sample Size

The MoCA scale was assessed in DLB subjects and reported in [Biundo et al. \(2016\)](#). The observed mean change from baseline in the MoCA total score at 1 year in this report is -1.04 points and the corresponding standard deviation (SD) is 1.32 points. An estimation of the mean change from baseline in the MoCA total score at 3 months is approximately -0.26 points using linear interpolation. It is assumed that E2027 would improve the MoCA total score as compared with baseline and achieve a mean treatment difference of approximately 0.6 points between E2027 and placebo at 12 weeks. The SD of change from baseline in the MoCA total score at 3 months is expected to be smaller than that at 1 year. A conservative estimate of the SD of change from baseline in the MoCA total score is 1.3 points at 12 weeks.

In a 12-week donepezil monotherapy study in subjects with DLB (E2020-J081-431), the estimated proportional odds ratio based CIBIC-Plus scale for donepezil 10 mg relative to placebo was 6.14. It is assumed that E2027 would achieve a proportional odds ratio of 2.607 relative to placebo (ie, 42% of the effect size observed in the above donepezil study).

With 80 subjects completing per arm (for 91 randomized subjects per arm, assuming a 12% dropout rate), this study will have approximately 80% power to detect the above effect sizes (ie, mean treatment difference of approximately 0.6 points based MoCA total score and proportional odds ratio of 2.607 based on CIBIC-Plus scale for E2027 relative to placebo) in both coprimary endpoints simultaneously. Therefore, the total sample size of 182 randomized subjects is planned, assuming a 12% dropouts rate.

Participation in the CSF substudy is voluntary. It is estimated that approximately 30% of subjects will participate in the CSF substudy. If the dropout rate in the CSF substudy is 12%, 20%, or 50%, then the number of subjects having final CSF assessment would be approximately 48, 44, or 27, respectively. The estimated standard deviation of percent change from baseline of cGMP concentrations after 9 weeks of treatment from pooled subjects in the CSF substudy is approximately 130%. The width of the 95% CI of treatment between E2027 and placebo for the 3 different sample sizes above would be approximately 74%, 77%, or 96%, respectively. Since mean percent change from baseline of cGMP concentrations after 9 weeks of treatment in the E2027 and placebo groups are expected to be approximately 200% and 5%, respectively, the sample size of the CSF substudy would be adequate to detect the mean difference of percent change from baseline in cGMP concentrations after 9 weeks of treatment between the E2027 and placebo groups.

9.7.3 Interim Analysis

This is a fixed design. There is no interim analysis of efficacy and no alpha spending before final analysis. (revised per Amendment 03)

An independent DSMB will convene at regular intervals to monitor the overall safety of the study and to make recommendations to the sponsor related to study safety as appropriate. The DSMB will be asked to review the cumulative safety data up to the date identified to make a determination if the study is safe to proceed unchanged or to provide recommendations to the

sponsor as to how to proceed. The study will proceed, including randomization of additional subjects, during DSMB safety reviews. Details will be provided in the DSMB Charter.

9.7.4 Other Statistical/Analytical Issues

Not applicable.

9.7.5 Procedure for Revising the Statistical Analysis Plan

If the SAP needs to be revised after the study starts, the sponsor will determine how the revision impacts the study and how the revision should be implemented. The details of the revision will be documented and described in the clinical study report.

11 PROCEDURES AND INSTRUCTIONS (ADMINISTRATIVE PROCEDURES)

11.1 Changes to the Protocol

Any change to the protocol requires a written protocol amendment or administrative change that must be approved by the sponsor before implementation. Amendments specifically affecting the safety of subjects, the scope of the investigation, or the scientific quality of the study require submission to health or regulatory authorities as well as additional approval by the applicable IRBs/IECs. These requirements should in no way prevent any immediate action from being taken by the investigator, or by the sponsor, in the interest of preserving the safety of all subjects included in the study. If the investigator determines that an immediate change to or deviation from the protocol is necessary for safety reasons to eliminate an immediate hazard to the subjects, the sponsor's medical monitor and the IRB/IEC for the site must be notified immediately. The sponsor must notify the health or regulatory authority as required per local regulations.

Protocol amendments that affect only administrative aspects of the study may not require submission to health or regulatory authority or the IRB/IEC, but the health or regulatory authority and IRB/IEC should be kept informed of such changes as required by local regulations. In these cases, the sponsor may be required to send a letter to the IRB/IEC and the Competent Authorities (or, if regionally required, the head of the medical institution) detailing such changes.

